#### 4. Background and Significance

*Chlamydia trachomatis* (CT), *Neisseria gonorrhoeae* (NG) and syphilis (caused by *Treponema pallidum*) infections are bacterial STIs that cause adverse neonatal outcomes. The risk of vertical

Title: The diagnosis and treatment of *Chlamydia trachomatis* and *Neisseria gonorrhoeae* in pregnant women to prevent adverse neonatal consequences.”

transmission of CT/NG during delivery is about 50%. Among infants born to mothers with untreated CT infection, 30–50% develop clinical conjunctivitis and 10-20% develop pneumonia due to CT. Among infants born to mothers with untreated NG infection, the risk of conjunctival infection is up to 48%, which can result in corneal damage and blindness. A recent study in South Africa found that among infants born to a mother with CT, NG, or *Trichomonas vaginalis* (TV) infections, 37% had nasopharyngeal colonization with the same STI organism. Other studies on CT/NG infections in neonates are over 20 years old. HIV-infected pregnant women with CT/NG infections are at increased risk of MTCT of HIV. Untreated syphilis during pregnancy is associated with increased risk for early fetal death, stillbirth, preterm birth, low birthweight, neonatal death, and clinical disease in infants. Congenital syphilis is the second leading cause of preventable stillbirth globally.

According to the WHO, CT, NG, and syphilis are the most common STIs globally with 131 million new cases of CT, 78 million new cases of NG infections, and 6 million new cases of syphilis annually. These infections are more common among people living with HIV. Despite the large burden of CT/NG infections and the above mentioned adverse outcomes, few countries have guidelines that recommend routine antenatal CT/NG testing. The WHO STI Treatment Guidelines are silent on the issue due to lack of evidence. In most low/middle countries, syndromic management (SM) is used to manage CT/NG infections. SM utilizes an algorithm to classify symptoms and clinical signs into STI syndromes, and patients are treated with standardized drug regimens. SM lacks specificity, causing unnecessary exposure to antibiotics, and has low sensitivity, missing the large proportion of asymptomatic infections and potentially putting neonates at risk for transmission. A study in Botswana found that among women with confirmed CT, NG, *Trichomonas vaginalis* (TV), only 10% reported vaginal discharge and 8% reported lower abdominal pain. In our pilot study, we found that less than 40% of women with etiologically diagnosed CT, NG, and TV infections reported having vaginal discharge, lower abdominal pain, and/or painful urination. Thus, it's possible that many infections are being missed among pregnant women in Botswana. Botswana national guidelines recommend universal screening and treatment of syphilis during pregnancy, which is conducted using the rapid plasma reagent (RPR) test or the venereal disease research laboratory (VDRL) with delayed results and treatment. However, a national surveillance study reported that only 59% of those with a reactive RPR were treated, and treatment was delayed by five weeks on average.

As accurate and rapid testing technology is increasingly affordable, more evidence on the benefits of antenatal CT/NG testing is needed. This study will utilize an innovative reverse transcription polymerase chain reaction (PCR) assay that can provide results within 90 minutes. Xpert® CT/NG also has high sensitivity (97.6% and 95.6% for CT/NG respectively) and specificity (99.4% and 99.8% for CT/NG respectively) and functions well in resource-constrained environments such as those proposed here. For syphilis testing, we will use WHO pre-qualified dual syphilis/HIV point-of-tests and rapid syphilis tests (SD Bioline), which will be offered in addition to the standard of care syphilis screening procedure.

The proposed study will estimate the prevalence and correlates of infection among pregnant women who present to antenatal care without STI-related symptoms, and thus would not be treated for infections through the standard care. We will assess the impact of antenatal CT/NG testing to prevent vertical transmission and associated adverse health outcomes compared to the standard of care. We will use markers of tissue inflammation specific to the Xpert® to explore the inflammatory responses to CT/NG and associations with vertical transmission. We will assess the acceptability, feasibility, and costs associated with PoC dual syphilis/HIV testing. We hope to inform stakeholders and policy makers as they work to improve management of STIs during antenatal care in order to improve maternal and neonatal outcomes.

We will include women aged 15-17 years, who are pregnant and receiving care, because pregnancy and curable sexually transmitted infections (STIs), such as *Chlamydia trachomatis*, *Neisseria gonorrhoeae* and syphilis are common among adolescents in Botswana. Recent research by BHP determined that of 737 adolescent females, aged 16-19 years, 340 (46%) reported being sexually

Title: The diagnosis and treatment of *Chlamydia trachomatis* and *Neisseria gonorrhoeae* in pregnant women to prevent adverse neonatal consequences.”

active. Of these, 121 (36%) reported having at least one child. A 2007 study of STIs among pregnant women in Gaborone, found that age was a strong predictor of *C. trachomatis* and/or *N. gonorrhoeae* infections; and, in a sample of 703 pregnant women, the prevalence of cervical infections was highest among teenagers (22%; 95% CI: 13-32%). Recent research in Southern Africa has similarly found that the prevalence of STIs was higher among younger women. Thus, in order to understand the burden and address the increased risks for STIs faced by women under 18 years, more research is needed among this group.

## 5. Characteristics of the Subject Population:

### a. Number of subjects / Sample size:

Pregnant women attending their first ANC care visit at 27 weeks gestation or less. Participants must be 15 years of age and not treated with azithromycin, doxycycline, cefixime, or ceftriaxone in the past 30 days.

**Specific Aim 1 (STI testing group):** We will recruit 250 study participants for CT and NG testing.

**Specific Aim 2 (Standard of care comparison group):** We will recruit 250 antenatal patients from designated study ‘standard of care’ clinics who will be enrolled as a comparison group receiving the standard care with additional IPV and partner services and postnatal care testing (Total N=500). Among participants who test positive during postnatal care, we will offer infant testing (Estimated N=30 infants).

For Specific Aims 1 & 2, study staff will remain at study clinics during operating hours for the duration of the recruitment period. We will consecutively screen all pregnant women for eligibility and offer enrollment to all eligible women.

**Specific Aim 3 (Inflammatory markers):** We will include women in the STI testing group (Estimated N=250).

**Specific Aim 4:** We will enroll an additional 400 antenatal patients for the PoC syphilis sub-study (200 will receive the standard of care and 200 will be offered PoC syphilis testing in addition to the standard of care)

### b. Inclusion/Exclusion Criteria:

#### • Inclusion Criteria:

- Age  $\geq$  15 years,
- Currently pregnant,
- Attending first ANC visit,
- 27 weeks gestation or less
- Not currently experiencing CT/NG-related symptoms (determined by validated screening tool),
- Not treated for CT/NG in the past 30 days,
- Willingness to provide self-collected specimens for CT/NG testing (for the STI-testing group, this will take place at their first ANC visit, at another visit in their third trimester,

Title: The diagnosis and treatment of *Chlamydia trachomatis* and *Neisseria gonorrhoeae* in pregnant women to prevent adverse neonatal consequences."

and at postnatal care. For the standard of care group, samples will only be collected at postnatal care),

- Willingness to return for a test of cure if CT/NG test is positive during antenatal care,
- Will reside in Gaborone through the time of delivery and 1st postnatal visit,
- Willingness to have neonates tested for CT/NG at their first postnatal visit,
- Mentally competent to understand the informed consent.

**• Exclusion Criteria:**

- Not mentally competent to understand study procedures or give informed consent,
- Individuals < 15 years,
- Men,
- Women who are not pregnant,
- Pregnant women not attending their first antenatal visit,
- Pregnant women at >27 weeks gestation
- Pregnant women with current STI-related symptoms (will receive standard of care),
- Treated for an STI in the past 30 days

**c. Determining Eligibility --- Study Screening:** Screening of prospective participants is confidential and will be undertaken by study personnel with training in ethical treatment of human subjects.

**d. Reasons for Exclusion:**

This study is designed to investigate benefits to women and infants of testing asymptomatic pregnant women for *Chlamydia trachomatis* and *Neisseria gonorrhoeae* during their first and third antenatal care visit. Therefore, women who are not pregnant as well as men are excluded from participation. Women with symptoms will receive syndromic management and those treated in the last 30 days are likely to be cured of STIs.

**e. Vulnerable Subjects:** As this study is conducted in Botswana, all interviews and exchange of information is conducted in English or Setswana. As the study concerns antenatal and postnatal testing, participants are pregnant women and infants.

**f. Inclusion of women aged 15-17 years:** As we are including participants under 18 years, we will add additional protections for minors such as: reporting requirements for abuse and referrals to social workers and added support for partner notification. We have also added an adolescent health expert to our team to advise on these issues.

**6. Subject Identification and Recruitment:**

**Specific Aim 1:** Patients will be screened for eligibility via obstetric chart review and brief screening questions at the time of the appointment. All eligible patients will be provided information about CT/NG infections and study risks and benefits. Those providing informed consent will be enrolled, instructed on how to self-collect a CT/NG specimen and asked to share several forms of detailed contact information to assure follow-up. Reasons for ineligibility will be logged with age, gestational age, and reason for ineligibility, to assess generalizability. Similar data and reasons for decline will also be recorded. A data collection instrument will be used to collect sociodemographic, behavioral, sex partner, obstetric, and medical information. Data will be abstracted both from patient medical records and interviews by study staff.

The sample of sex partners will be recruited through the following channels a) snowball recruitment via study participants who give informed consent to contact their partner(s) b) sex partners presenting

Title: The diagnosis and treatment of *Chlamydia trachomatis* and *Neisseria gonorrhoeae* in pregnant women to prevent adverse neonatal consequences.”

to a study clinic for STI treatment using a contact slip c) sex partners contacting the study team via contact information included with EPT materials (with permission of index patient) d) partners attending antenatal or postnatal care visits with partners.

The sample of stakeholders will be recruited through email, word of mouth and visits to study clinics.

**Specific Aim 2:** Women in the Standard of Care group will be similarly recruited and enrolled, and eligibility criteria are identical to those in the STI testing group (see Aim 1). All eligible patients will be invited to participate, and those providing informed consent will be enrolled. The Standard of Care group will receive the standard of care in Botswana for the management of STIs with additional intimate partner violence (IPV) screening and partner services offered to those in Aim 1. As in Aim 1, a data collection instrument will be used to collect sociodemographic and behavioral factors, and obstetric/medical information. All mothers will be provided with informed consent for their neonate’s participation at enrollment. Postdelivery, study staff will provide an updated verbal consent to mothers to collect and tests neonatal specimens.

**Specific Aim 3** At the baseline, third trimester and postnatal care study visit, self- collected swabs  and plasma samples (2-4mL) will be collected from participants in the STI testing group, and used to measure cytokine concentrations. Cytokines will be identified using the Luminex xMAP® 48-plex assay method located at Stanford University in order to test immunologic factors associated with vertical CT/NG transmission by describing concentrations of inflammatory cytokines in participants who tested positive for CT/NG. We will also conduct a secondary analysis of data collected during maternal CT/NG testing at the first postnatal visit (Aim 2) will be performed to determine the association between the Xpert® CT/NG assay’s pathogen-specific cycle threshold value ( $C_t$ ), which is a marker for the burden of infection, and vertical transmission of CT/NG to neonates; and assess the frequency and distribution of Sample Adequacy Control (SAC) cycle threshold ( $C_t$ ) values from the Xpert® CT/NG assay, which may be a marker of inflammation, and evaluate correlations with the transmission of CT/NG to neonates.

**Specific Aim 4:** Women in the syphilis sub-study will be similarly recruited and enrolled as in Aim 1 and 2. All participants will receive the standard of care in Botswana for syphilis testing with additional IPV screening and partner services offered to those in Aims 1 and 2. A simplified data collection instrument will be used to collect sociodemographic and behavioral factors, and obstetric/medical information with additional questions related to patient costs incurred due to syphilis care. Participants recruited into the PoC syphilis testing clinic will provide a blood sample for PoC syphilis testing and treatment.

## 7. Methods and Procedures applied to human subjects

### a. Study Protocol used by study personnel at Greater Gaborone DHMT Clinics:

#### Enrolment, follow up visits and sample collection

- All participant recruitment will occur in up to eight DHMT clinics in Greater Gaborone. Study staff will be trained in the study’s methods, protocol, and human subjects research, and will conduct eligibility screening on all patients attending their first ANC visit, following a simple, standard checklist of eligibility criteria. Staff will read all eligible women a brief description of the study. Interested women will then be read aloud the study consent form in their preferred language, which will provide specific information about sexually transmitted infections, the consequences and treatment of those infections, and study risks and benefits, and then will be invited to participate in the study. Staff will collect basic

Title: The diagnosis and treatment of *Chlamydia trachomatis* and *Neisseria gonorrhoeae* in pregnant women to prevent adverse neonatal consequences.”

de-identified information from clinic logs (i.e., age, gestational age, HIV status) to use for descriptive analysis of the general ANC patient population.

- Study personnel will inform potential participants about the risks and benefits of study participation and answer any questions they may have concerning the study protocol. Study personnel will then ask interested eligible women sign an informed consent for participation (consent form in appendix).
- To ensure retention, those providing informed consent will be asked to provide detailed contact information (e.g., phone numbers and “home address” for self, family, friend/neighbor) to ensure follow-up. To develop and maintain a strong relationship with participants, study staff will conduct welcome phone calls within 3 days of enrollment, and check in with participants during regular ANC clinic visits. Clinic and study staff will contact participants who do not return for scheduled ANC visits and encourage return for care. We will flag participant charts so that clinic staff will notify study staff on the date of delivery.
- During the antenatal visits (1st antenatal care and a visit in the 3rd trimester), participants in the STI testing group will be asked to provide self-administered vaginal swab samples for CT/NG testing by the GeneXpert and cytokine testing by Luminex. Participants will also be asked to provide additional samples that will be stored for testing of *Trichomonas vaginalis*, bacterial vaginosis, and/or *Mycoplasma genitalium*. These samples will be stored at the BHP lab for no longer than 24 months. Participants will also be asked to provide a plasma sample, collected by a trained phlebotomist, for cytokine testing by Luminex.
- During the first antenatal visit, a sub-sample of participants in the standard of care group will be asked to provide two self-administered vaginal swabs for testing after study completion. These samples will be immediately de-identified and stored at the BHP lab for no longer than 24 months.
- During the 1st antenatal care visit, participants in the syphilis PoC clinic will be asked to provide a blood sample for either dual HIV/syphilis or rapid syphilis point-of-care testing, which is offered in addition to the standard of care.
- During postnatal care, all participants will self-collect a vaginal sample for CT/NG testing by the GeneXpert. Participants in the testing group will self-collect an additional vaginal sample and will provide a plasma sample for cytokine analysis. Those who test positive will be offered infant testing via ocular/nasopharyngeal samples. Infant samples will be collected by a trained study nurse. Participants will also be asked to provide additional samples at the postnatal visit that will be stored for testing of *Trichomonas vaginalis*, bacterial vaginosis, and/or *Mycoplasma genitalium*. These samples will be stored at the BHP lab for no longer than 24 months.
- Postnatally, a sub-set of 35 participants who were treated for CT/NG, an STI syndrome or syphilis at any point during the study will be asked additional questions by study staff, expanding on partner

Title: The diagnosis and treatment of *Chlamydia trachomatis* and *Neisseria gonorrhoeae* in pregnant women to prevent adverse neonatal consequences."

notification and treatment experiences. These patients will additionally be asked if they are willing to refer their partner to participate in a semi-structured interview. If so, they will sign an informed consent allowing the study team to contact their partner(s).

- Specimens for CT/NG and syphilis testing will be processed onsite at the antenatal clinics by study personnel.
- Specimens for *Trichomonas vaginalis*, bacterial vaginosis, and/or *Mycoplasma genitalium* testing will be stored for up to 24 months at BHP.
- The self-collected swabs and EDTA plasma aliquots for cytokine measurement will be stored at -80 C. The swabs and EDTA plasma will be transported in dry ice to Stanford University for processing. Luminex will be used to measure the concentrations of 48 cytokines (including IL-1a $\pm$ , IL-1b $\leq$ , IL-6, IL-7, IL-8, IL-10, granulocyte macrophage colony- stimulating factor [GM-CSF], interferon- $\gamma$  inducible protein [IP]-10, monocyte chemoattractant protein [MCP]-1, MIP-1a $\pm$ , MIP-1b $\leq$ , and tumor necrosis factor [TNF]-a $\pm$ ). These cytokines were selected based on previously identified associations with genital infection.(34) Additionally the pathogen-specific and SAC Ct results will be automatically generated for each self-collected vaginal swab sample tested using the Xpert CT/NG assay at the first postnatal visit.

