Title: The diagnosis and treatment of *Chlamydia trachomatis* and *Neisseria gonorrhoeae* in pregnant women to prevent adverse neonatal consequences.”

CT/NG to neonates; and 3(c): To assess the frequency and distribution of Sample Adequacy Control (SAC) cycle threshold ( $C_t$ ) values from the Xpert® CT/NG assay, which may be a marker of inflammation, and evaluate correlations with the transmission of CT/NG to neonates.

**Recruitment/Eligibility:** Eligibility criteria for the comparison group are identical to those in Aims 1 and 2. Data will only be collected from participants in the STI testing group.

**Specimen Collection, Transport, Processing and Storage:** A self-collected swab for cytokine measurement will be collected at the baseline, third trimester, and first postnatal care visit and stored at -80°C. A peripheral blood sample (2-4mL) will be collected at the baseline, third trimester, and postnatal study visits. The blood sample will be processed and aliquots of EDTA plasma will be stored at -80°C. The swabs and plasma samples will be transported in dry ice to Stanford University for processing. Luminex will be used to measure the concentrations of 48 cytokines in the 48-plex assay (including IL-1 $\alpha$ , IL-1 $\beta$ , IL-6, IL-7, IL-8, IL-10, granulocyte macrophage colony- stimulating factor [GM-CSF], interferon- $\gamma$  inducible protein [IP]-10, monocyte chemoattractant protein [MCP]-1, MIP-1 $\alpha$ , MIP-1 $\beta$ , and tumor necrosis factor [TNF]- $\alpha$ ). These cytokines were selected based on previously identified associations with genital infection. Additionally the pathogen-specific and SAC Ct results will be automatically generated for each self-collected vaginal sample tested using the Xpert® CT/NG assay at delivery.

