Statistical Plan: Evaluating the diagnosis and treatment of *Chlamydia trachomatis* and *Neisseria gonorrhoeae* in pregnant women to prevent adverse neonatal consequences in Gaborone, Botswana

ANALYSIS

Primary outcome measure

- Mother-to-child transmission of CT and/or NG: Neonates of mothers who test positive for CT and/or NG infections will be tested using both ocular and nasopharyngeal specimens.

Secondary outcome measures

- Pregnancy outcome
 - o Miscarriage, defined as pregnancy loss before the 20th week of gestation, will be identified through self-report by the participants, and the medical record.
- Perinatal outcome
 - o Stillbirth, defined as fetal death at or after 20 weeks gestation and prior to delivery, will be identified through self-report by the participants, and the medical record.
- Neonatal outcomes
 - o Preterm birth, defined as delivery prior to 37 weeks' gestation, will be identified through the obstetric record and/or
 - o Low birth weight, defined as birth weight of less than 2500g, will be identified through the obstetric record.
 - o Conjunctivitis, defined as the presence of swollen eyelids and pus in eyes, will be identified during the care visit by the follow-up nurse/midwife.
 - o Pneumonia, defined as cough or difficult breathing plus at least one of the following: Fast breathing, Lower chest wall indrawing. In addition, either crackles or pleural rub may be present on chest auscultation.
 - o We will also ask mothers about prior neonatal symptoms and review the obstetric record.
- Maternal outcomes
 - o CT and NG infections: The prevalence of maternal CT/NG infections will be assessed among participants in the testing group at baseline and during the third trimester.
 - o The incidence of infections between baseline and follow-up in the testing group.
 - o Individual cytokines and groups of cytokines associated with mother-to-child transmission of CT/NG, preterm birth, and low birth weight.
- Economic outcomes
 - o The total cost of the CT/NG test and treatment intervention for asymptomatic pregnant women.
 - o The costs per woman tested, treated, and cured; and the incremental costs per adverse neonatal outcome averted (e.g. neonatal CT/NG infections, preterm birth, and low birth weight) comparing the testing intervention with syndromic management.

Statistical analysis

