Prevalence of each STI will be measured as the proportion of individuals testing positive for a given STI divided by the number of individuals tested at each time point. Exact binomial 95% confidence intervals for prevalence will be estimated. Incident infections will be identified when a participant tests negative for an STI during her first ANC visit and positive for an STI during follow-up visits. Time at risk will be the length of time between the first test date and the positive test date. Correlates of CT/NG infections will be identified using both bivariate analyses and multivariate analyses.

Our primary outcome (mother-to-child transmission of CT and NG) and secondary outcomes (composite of preterm birth and/or low birth weight, and prevalence of maternal CT/NG infection at delivery) will be assessed using intention to treat analysis at the clinic level. We will conduct both unadjusted and adjusted analyses, including risk factors for maternal STI and neonatal infection that may be imbalanced between the testing and standard-of-care clinics. Effect measures will be estimated with 95% confidence intervals. All analyses will be carried out using the latest version of Stata statistical software (17.0 or higher; College Station, TX, USA).

To assess immune/inflammatory markers, multiple logistic regression models will be developed in an iterative process to identify individual cytokines and groups of cytokines associated with mother-to-child

transmission of CT/NG, preterm birth, and low birth weight. Additionally, we will identify plasma cytokine signatures that classify study participants with or without preterm birth/low birth weight infants.(1) We will define three equal frequency tertiles or “bins” (low, medium, and high), using all plasma samples. Next, we will use the VSURF R package, a random forest method to select the most predictive cytokines to differentiate samples from participants with and without preterm birth/low birth weight infants.(2) From these, we will build a decision tree to classify the samples. To better calibrate the accuracy of the decision tree, we will perform permutation testing.

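### The cytokine models for preterm birth and low birth weight name neither the visit nor gestational age at sampling, so a cytokine that only tracks gestation can appear associated with the outcome

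*Protocol*

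**What the plan says.** **Sampling.** Under Specific Aim 3 in Protocol section 3: "A peripheral blood sample (2-4mL) will be collected at the baseline, third trimester, and postnatal study visits". Section 7a repeats the plan for the antenatal visits: "Participants will also be asked to provide a plasma sample, collected by a trained phlebotomist, for cytokine testing by Luminex". Neither place gives a week range for the third-trimester visit. The only gestational limit is the inclusion criterion, "27 weeks gestation or less", which governs enrolment and therefore the first sample.

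**Outcomes.** The SAP's secondary outcomes include "Preterm birth, defined as delivery prior to 37 weeks' gestation" and "Low birth weight, defined as birth weight of less than 2500g". The second definition has no gestational condition, so a term infant can meet it.

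**Analysis.** The SAP's section on statistical analysis says that "multiple logistic regression models will be developed in an iterative process to identify individual cytokines and groups of cytokines associated with" transmission, preterm birth and low birth weight. Separately, plasma cytokines are cut into tertiles formed from every plasma sample. A random-forest step (VSURF) is then used "to select the most predictive cytokines to differentiate samples from participants with and without preterm birth/low birth weight infants", followed by a decision tree and permutation testing. No visit, covariate or gestational-age term is named for any of these models. The SAP's sentence on adjusted analyses concerns imbalance between testing and standard-of-care clinics; the cytokine work uses the testing group only.

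**Gestational age** is collected. Its stated uses are screening logs, description of clinic patients, and monitoring of balance between clinics.

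**The concern.** The outcome partly determines when a woman can be sampled. A third-trimester sample exists only if the visit comes before delivery. Women who deliver early therefore drop out of the later sampling dates, and those who remain were sampled earlier on average. A cytokine whose level changes with gestation will then differ between preterm and term deliverers even if it has no relation to preterm birth. For preterm birth alone, a sample taken at 37 weeks or later cannot come from a case.

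At stake is whether a reported cytokine association or signature reflects risk of early delivery or only how far the pregnancy had advanced when blood was drawn. The planned permutation test would not tell these apart: shuffling outcome labels freely also breaks the link between outcome and sampling date that creates the bias.

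**Working it through.** **Figure to reproduce.** None. The documents give no power, error rate or precision for the cytokine models; the SAP's one power figure concerns the primary endpoint.

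**Inputs from the documents.** Testing group 250 (Protocol 5a); 232 evaluable after 7% loss (SAP, sample size); preterm means delivery before 37 weeks; no week limits on the third-trimester visit; 48 cytokines (Protocol, Aim 3).

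**Inputs assumed, because the documents give none.** Preterm risk 15%. Preterm delivery at 37 minus a gamma(shape 1.3, scale 2.2) number of weeks. Term delivery about 39.3 weeks (SD 1.1), not before 37. Visit date uniform over a stated range. Cytokine = slope × gestational age at sampling + N(0,1), with no link to preterm birth. For the composite, 7% term low birth weight. The ranges below are illustrations, not proposed visit windows.

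**Step 1, structure.** Let s be the week of the visit and D the week of delivery. A sample exists only if s < D, and preterm means D < 37. So s ≥ 37 implies not preterm. For the composite, s ≥ 37 can still be a case through term low birth weight.

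**Step 2, who is sampled (visits over 28-38 weeks).** Mean preterm delivery is 37 − 1.3 × 2.2 = 34.14 weeks. The expected share of preterm deliverers with no third-trimester sample is about (38 − 34.14)/10 = 39%; simulation gives 38%. Mean gestation at sampling is 31.5 weeks in preterm and 33.0 in term deliverers, and 9% of samples fall at 37 weeks or later. If visits end by 34 to 36 weeks, 14-24% of preterm deliverers still lack the sample.

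**Step 3, false positives.** Share of simulated trials in which one cytokine, related only to gestation, reaches p < 0.05 in a logistic model (third-trimester samples; ranges span separate runs):

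| Visits (weeks) | Drift (SD/week) | Preterm, gestation omitted | Preterm, gestation included | Composite, gestation omitted |
|---|---|---|---|---|
| 28-38 | 0.1 | 8-9% | 4-5% | 7-8% |
| 28-38 | 0.2 | 17-19% | about 5% | 13% |
| 28-36 | 0.2 | 8% | 5% | 6.5% |
| 28-40 | 0.2 | 29% | 4% | not run |

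For visits ending by 34 to 36 weeks the preterm rate is 4-8% overall; the composite gives about 4% for 28-34 weeks. With 1,000 runs the simulation standard error at 5% is √(0.05 × 0.95/1000) = 0.7 points.

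**Step 4, what the drift means.** Over 28-38 weeks the SD of visit date is 10/√12 = 2.89 weeks. Drift 0.2 gives a correlation of 0.577/√(1 + 0.577²) = 0.50 between cytokine and gestation; drift 0.1 gives 0.289/√(1 + 0.289²) = 0.28.

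**Step 5, second parameterisation.** A separate simulation set the correlation directly and spread visits over 28-40 weeks. At 15% preterm risk the unadjusted rate was about 12%, 20-22% and 35-39% for correlations 0.3, 0.5 and 0.7, about 5% at correlation 0, and 4-7% with gestational age in the model in every setting tried. For the composite (5-8% term low birth weight assumed; visits over 28-40 or 32-40 weeks) it was 14-28% at correlations 0.5-0.7. About 2 to 3 of some 35 samples at 37 weeks or later (28-40 weeks) were composite cases.

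**Step 6, parts of the remedy.** Dropping samples at 37 weeks or later without adjusting still leaves 9-10% at drift 0.2. Adjustment is what restores about 5%. Pooling first-visit and third-trimester samples makes the problem worse: 11% and 20% at drifts of only 0.05 and 0.1 (visits over 28-38 weeks), again about 5% with adjustment.

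**The case against.** Several objections have force.

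- *The SAP does not rule out adjustment.* A reader might infer that the plan has decided to ignore gestational age. The text does not support that: it names no covariates for any cytokine model, and the logistic models are multivariable. This stands. But iterative model building with no forced terms gives no assurance that gestational age will be included.
- *Late samples are not certain non-cases everywhere.* It is tempting to say that samples at 37 weeks or later flatter the classifier with women who could not be cases. VSURF and the tree classify the composite, and low birth weight can occur at term, so that is wrong for the classifier. It is exact only for preterm birth taken alone. The bias for the composite is weaker but present.
- *The size rests on unseen inputs.* This stands. Appreciable inflation needs both late visits and marked drift. Visits are tied to routine antenatal care and may end earlier, where the rate is near nominal.
- *The classifier was not simulated.* This also stands. The figures are for single-cytokine logistic tests; no VSURF, tree or tertile analysis was run, nor low birth weight alone, and the SAP states no p < 0.05 rule for cytokines.
- *Multiplicity is the larger problem.* With 48 independent tests at 5%, the chance of at least one false positive is 1 − 0.95^48, about 91%. That is true, but chance findings tend to fail on replication, whereas a gestational-age artefact would recur in any study sampled the same way.

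**Conclusion.** The concern holds for the cytokine analyses of preterm birth and low birth weight. The third-trimester sample has no stated week limits, plasma samples are pooled across visits for binning, and gestational age at sampling is not mentioned, although delivery timing governs when or whether a woman is sampled.

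With 15% preterm, visits over 28-38 weeks and drift 0.1-0.2 SD per week, the per-marker false-positive rate is about 8-19% for preterm birth and 7-13% for the composite, against about 5% with adjustment. It falls to about 4-8% if visits end by 34 to 36 weeks, and there is no inflation for a cytokine that does not drift. Preterm risk, visit dates and drift are all assumptions, so the documents do not show that false signals will be reported, only that the plan has no protection against them.

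These are secondary analyses. A reader should not infer any effect on the primary endpoint or its power, which do not use cytokines.

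**What to change.** In the SAP's paragraphs on immune and inflammatory markers:

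1. Analyse first-visit and third-trimester samples separately, naming the visit used in each model.
2. Force gestational age at sampling into every cytokine logistic model for preterm birth and low birth weight.
3. Account for it in the classifier as well, for example by replacing each cytokine with its residual on gestational age at sampling before tertile binning, VSURF and the tree. This step has not been tested here.
4. For the preterm-only models, also exclude samples taken at 37 weeks or later. This supplements adjustment and does not replace it.
5. Report, by outcome, how many women had no third-trimester sample because they had already delivered. Adjustment does not recover these women, so the number is needed to interpret the result.

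No new data or visits are needed: gestational age at each sample is enrolment gestational age plus the days from enrolment to sampling divided by 7. The cost is a few sentences, one degree of freedom per model, and the loss of a few late samples from the preterm-only models (9% of third-trimester samples in the 28-38 week illustration).
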